## 2.2 Study setting and participants

The participants will be recruited from August 2023 to July 2026 and followed up for eight weeks at a medical center in northern Taiwan.

Recruited criteria were: (1) outpatients with DFUs over 20 years old; (2) can be interviewed in Mandarin or Taiwanese.

The exclusion criteria were: patients (1) planning to return visits within eight weeks less than two times; (2) without using a smartphone; (3) being unable to read text messages on a mobile phone or with impaired hearing; (4) with impaired fine hand movements; (5) unwilling to use the communication software LINE to receive text messages.

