### 2.6.2 Whether the Wound Shrinks

This study will measure the wound size at baseline, four and eight weeks. Then, whether the wound has shrunk will be determined by subtracting the pre-measurement area from the post-measurement area.

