## 2.7 Data collection

Before the study delivery, we will perform block randomization of four categories according to the statistical software (Sealed Envelope Ltd., 2022), with four as the block, and create label categories and case acceptance order according to the software allocation group, then putting the group name into the envelope. This study adopted categorical random allocation, with four categories: patients with neuropathic foot ulcers who received hemodialysis, patients with neuropathic foot ulcers who did not receive hemodialysis, patients without neuropathic foot ulcers who received hemodialysis, patients without neuropathic foot ulcers who did not receive hemodialysis.

After the research subjects agree to participate, the project leader will open envelopes to arrange their group location. Then, the data collection begins, including basic information on the research subjects, self-care behavior for diabetes, foot, and diabetic foot ulcers, self-efficacy in preventing and treating foot ulcers, quality of life, and wound measurement. Two post-tests (questionnaire interview and wound

assessment) will be conducted four and eight weeks after baseline data collection.

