## 2.8 Data analysis

The data will be analyzed with SPSS statistical software for Windows 20.0 (SPSS, Inc., Chicago, IL, USA). The chi-square and Mann-Whitney U tests will be used to determine the homogeneity between the intervention and control groups. An intention-to-treat analysis approach (ITT) will be used. Generalized estimating equations (GEEs) will be used to examine the effects of intervention measures on improving the study subjects' self-care behavior, self-efficacy, and quality of life. The chi-square test will be used to detect whether there was any difference in the proportion of wounds reduced by 50% or more between the two groups of study subjects four weeks after admission.

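### No study ulcer is fixed before allocation and the unit of the week-4 wound test is ambiguous, so it is open either to correlated observations or to an ulcer chosen with the arm known

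*Combined protocol and SAP*

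**What the plan says.** Section 2.2 admits "outpatients with DFUs over 20 years old". The five exclusions concern return visits, smartphone use, reading or hearing, hand movement and the messaging application; none limits the number of ulcers.

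Section 2.6.2 states: "This study will measure the wound size at baseline, four and eight weeks". It then derives shrinkage by subtracting areas. It is written in the singular, and gives no index ulcer, no total-area rule and no rule for several ulcers.

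Section 2.7 randomises patients within four strata. On the order of events it says: "After the research subjects agree to participate, the project leader will open envelopes to arrange their group location". The next sentence opens with "Then, the data collection begins", and wound measurement is among the items it lists.

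Section 2.8 applies a chi-square test at four weeks to find out "whether there was any difference in the proportion of wounds reduced by 50% or more between the two groups of study subjects". GEE is reserved for the behaviour, self-efficacy and quality-of-life scores, so no method for correlated wounds is given.

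**The concern.** The unit randomised is the patient. The unit in the wound test, as worded, is the wound. For a patient with one ulcer the two coincide. For a patient with two, the plan does not say what to do, and two of the permitted choices damage the comparison in different ways.

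- If both ulcers are entered, the chi-square treats two related outcomes as independent. Its standard error is then too small, and the patient counts twice although randomised once.
- If one ulcer is entered, nothing stops it being picked after the allocation is known, because measurement follows the envelope and no blinded assessor is described.

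These are alternatives, not a combined effect: counting every ulcer leaves no choice to make, and choosing one leaves no within-patient correlation. Wound prognosis is among the aims in the Introduction, and this chi-square is the only between-arm wound test that the plan specifies.

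**Working it through.** **The plan's own figure.** There is none for the wound test. The sample size of 178 in section 2.3 is for quality of life, and nothing below depends on it.

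**Permitted readings for a patient with two baseline ulcers**

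| Reading | Textual support | Consequence |
|---|---|---|
| Every ulcer counted | 2.8 tests a proportion of wounds | Correlated observations |
| One ulcer counted | 2.6.2 is written in the singular | Choice possible with the arm known |
| Total area per patient | 2.6.2 works with area | Neither problem |

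The plan does not choose among the three.

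**Size under the first reading**

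Assumed inputs, not in the documents: a fraction f of patients has two ulcers and the rest have one, with f from 0.15 to 0.30; the within-patient correlation of response, r, is 0.3 to 0.8; f and r are the same in both arms.

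1. Mean cluster size weighted by wounds = (sum of m²)/(sum of m) = (1 + 3f)/(1 + f).
2. Design effect DE = 1 + [(1 + 3f)/(1 + f) − 1] × r = 1 + [2f/(1 + f)] × r.
3. Actual two-sided error of a nominal 5% test = 2 × [1 − Φ(1.96/√DE)].

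| f | r | 2f/(1 + f) | DE | Actual error |
|---|---|---|---|---|
| 0.05 | 0.3 | 0.095 | 1.029 | about 0.053 |
| 0.15 | 0.3 | 0.261 | 1.078 | 0.059 |
| 0.30 | 0.5 | 0.462 | 1.231 | 0.077 |
| 0.30 | 0.8 | 0.462 | 1.369 | 0.094 |

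The first row lies below the assumed range and shows how small the effect is when few patients have two ulcers. Widening the assumptions to f from 0.10 to 0.50 and r from 0.2 to 0.8 gives errors from 0.054 to 0.114.

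The quantity 2f/(1 + f) is also the share of analysed wounds that come from patients with two ulcers. At f = 0.30 these patients supply 46% of the wounds.

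**Size under the second reading**

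The bias depends on how many patients have several ulcers, how differently those ulcers heal, and how well the person choosing can foresee it. The documents give none of these.

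**The case against.** The strongest reply is that section 2.8 is loosely worded. The title and text of 2.6.2 refer to one wound, and 2.8 compares groups of study subjects, so the intention may be one result per patient. This stands as far as it goes. A reader might infer from 2.8 that a wound-level test is definitely planned and that the unit analysed does not match the unit randomised; the documents do not support that, because it is true under only one of three readings. But the reply leaves open which ulcer is the one wound, and when it is picked.

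Three other strong inferences also fail.

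- **New ulcers.** An ulcer that appears during follow-up has no baseline area, so it cannot be scored as halved at week 4. The correlation problem concerns baseline ulcers only.
- **A figure for selection.** Suppose a 40% response rate, 20% of patients with two ulcers, correlation 0.3, and the better ulcer always reported in one arm only. The chance that at least one of two ulcers responds is 2(0.40) − [0.40² + 0.3 × 0.40 × 0.60] = 0.568. The arm's rate becomes 0.8 × 0.40 + 0.2 × 0.568 = 0.434, a false difference of 3.4 points. That requires the week-4 outcomes to be known or perfectly predicted. A pick at baseline does not have them, so this is an extreme case, not an estimate.
- **The rest of the trial.** Quality of life, on which the sample size rests, and the other scales are measured per patient and are unaffected.

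It is also fair to say that ulcer type must be known before the envelope is opened, because it defines the strata. That does not fix which ulcer will be followed, and measurement still comes afterwards.

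**Conclusion.** The point holds as an ambiguity with consequences. The plan admits patients with several ulcers, fixes no study ulcer, opens the envelope before measuring, and words its only specified wound test in terms of wounds.

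On the literal reading, the nominal 5% error becomes about 5.9-9.4% under the assumed 15-30% of patients with two ulcers and correlation 0.3-0.8. The upper figure needs both upper ends, and the inflation is slight if few patients have two ulcers. On the one-ulcer reading, selection with the arm known is possible, but its size cannot be derived from the documents. No evidence in the documents shows that either has happened. The matter is confined to the week-4 wound comparison and should be settled because that comparison serves a stated aim.

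**What to change.** **Section 2.7.** Before the envelope is opened, identify and measure one study ulcer per patient by a fixed rule and record it. An example is the largest baseline area, with ties broken by the longest-standing ulcer.

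**Section 2.8.** Test the proportion of patients whose study ulcer area is reduced by 50% or more at four weeks. Describe other ulcers and new ulcers separately. With one observation per patient, the design effect is 1 and the clustering problem disappears.

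**Patients already enrolled.** Recruitment was planned from August 2023, so there may be some. Apply the same rule to recorded baseline areas without reference to arm, where all ulcers were measured. Where they were not, say so in the report.

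Leave the randomisation strata unchanged.

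**Cost.** A few sentences, a form field, and moving the baseline wound measurement ahead of allocation. Ulcers are already classified by type at that point, so identifying one adds little work. The downside is that other ulcers do not contribute to the main wound comparison. Keeping every ulcer in a patient-clustered GEE would deal with the correlation, but would still need a rule for which ulcers count.

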## INTRODUCTION

Diabetic foot ulcers need complex treatment and have poor prognoses. Thus, they consume medical resources and impede patients' quality of life. Most of the time, patients are required to perform diabetic foot ulcer self-management at home. However, their self-management behaviors are inadequate.

Individualized patient education messages can promote and maintain appropriate diabetes self-management behaviors. The short message-based customized standardized patient education program combines several smartphone message-based standardized educational contents to construct a customized patient education program that is according to patients' needs, thus promptly providing individualized patient education. The short message-based customized standardized patient education program may improve diabetic foot ulcer self-management behavior and self-efficacy on diabetic foot ulcer self-management, thereby promoting wound healing and improving quality of life.

This study aims to develop a short, message-based, customized standardized education program and to test the effect of the program on diabetic foot ulcer self-management behavior, self-efficacy, wound prognosis, and quality of life.

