## 2.3 Sample size and statistical power

In this study, we will use the generalized estimating equation (GEE) to detect the effectiveness of intervention in improving the quality of life. Since no previous research results are available for reference, we assume that the intervention in this study has a moderate effect. We set the effect amount as 0.25, the statistical power as 0.95, the alpha value as 0.05, and the number of repeated measurements as 3. The G\*power 3.1 statistical software shows that the required sample size was 178.

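### The only planned wound test is an unadjusted week-4 chi-square: valid, but it leaves out the stratification factors and baseline area, and the week-8 areas have no planned analysis

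*Combined protocol and SAP*

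**What the plan says.** - **Aim (Introduction).** The trial is to test the "effect of the program on diabetic foot ulcer self-management behavior, self-efficacy, wound prognosis, and quality of life".
- **Measurement (2.6.2).** The study will "measure the wound size at baseline, four and eight weeks". It adds that "whether the wound has shrunk will be determined by subtracting the pre-measurement area from the post-measurement area". No percentage, denominator or deciding visit is given.
- **Analysis (2.8).** The one wound test is a chi-square for a difference in "the proportion of wounds reduced by 50% or more between the two groups of study subjects four weeks after admission". The GEE models cover "self-care behavior, self-efficacy, and quality of life"; wound outcomes are not listed. Intention-to-treat is named, without a rule for missing wound areas.
- **Randomisation (2.7).** The plan uses "block randomization of four categories", formed by crossing neuropathic ulcer with hemodialysis. On the order of events: "the project leader will open envelopes to arrange their group location. Then, the data collection begins". Wound measurement belongs to that data collection. Follow-up at four and eight weeks is timed from baseline data collection.
- **Sample size (2.3).** The 178 patients are chosen for a GEE to "detect the effectiveness of intervention in improving the quality of life". No power is stated for the wound outcome.

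**The concern.** Baseline area, neuropathic ulcer and hemodialysis are all known for every patient, and any of them may predict whether a wound halves in four weeks. If they do, the unadjusted test gives up power at no saving. Two of them also define the randomisation strata, so the analysis does not reflect the design.

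Three gaps in the text add to this:

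- The final-visit wound areas have no stated role, so any week-8 comparison would be unplanned.
- The percentage that 2.8 needs is not defined in 2.6.2.
- Baseline area is the denominator of the outcome, and it is measured after the allocation has been revealed. A wound succeeds when follow-up area is at most 0.5 × baseline area, so overstating baseline by some percentage raises the cut-off by the same percentage.

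**Working it through.** **1. Definition against analysis.** Section 2.6.2 yields a difference in area. Section 2.8 needs 100 × (baseline − follow-up)/baseline ≥ 50. As an illustration, a wound going from 4.0 to 3.0 cm² has shrunk, but by 100 × (4.0 − 3.0)/4.0 = 25%, so it is not a success in 2.8.

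The documents give no wound data, so how often this happens must be assumed. If the log ratio of follow-up to baseline area is normal with mean m and SD s, the share that shrinks by less than half is Φ(−m/s) − Φ((ln 0.5 − m)/s).

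- m = −0.35, s = 0.6: 0.720 − 0.284 = 0.436
- m = −2, s = 0.6: 0.9996 − 0.9853 = 0.014

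Over m from 0 to −2 and s from 0.6 to 1.2 the share runs from about 1% to 44%. It depends wholly on these inputs.

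**2. Visits against analyses.** Areas are collected at weeks 4 and 8 (2.6.2, 2.7). Section 2.8 has one wound test, at week 4, and its GEE list has none. Week 8 is therefore unanalysed.

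**3. Size of the comparison.** The plan has no wound power figure to reproduce, so I took 178 as 89 per group. Assumed: 50% control success and a conditional odds ratio of 2.3. With non-prognostic covariates, intervention success is 2.3/3.3 = 0.697. Then:

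- pooled proportion (0.500 + 0.697)/2 = 0.5985
- null SE = √(2 × 0.5985 × 0.4015/89) = 0.0735
- alternative SE = √((0.25 + 0.697 × 0.303)/89) = 0.0720
- power = Φ((0.197 − 1.96 × 0.0735)/0.0720) = Φ(0.736) = 77%

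**4. Effect of adjustment, by simulation.** All inputs are assumptions except n, the four strata and the block size of four: 50% neuropathic, 20% hemodialysis, standard normal log area, complete data. The log-odds effect of each factor, and per SD of log area, is 0, 0.5 or 1.0. Run A has 8,000 trials per setting and takes the week-4 contrast from a logit GEE over both visits. Run B has 3,000 trials per setting and week-4 data only.

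| Covariates | Run | Chi-square | Strata only | Strata + log area | Gain over chi-square |
|---|---|---|---|---|---|
| Not prognostic (0) | A | 77.4% | 77.2% | 77.1% | −0.3 |
| | B | 77% | 77% | 76% | −1 |
| Moderate (0.5) | A | 71.3% | 71.9% | 74.0% | +2.7 |
| | B | 73% | 74% | 75% | +2 |
| Strong (1.0) | A | 57.2% | 59.6% | 66.8% | +9.6 |
| | B | 58% | 60% | 68% | +10 |

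Monte Carlo error near 70% power is √(0.7 × 0.3/8,000) = 0.5 points for A and √(0.7 × 0.3/3,000) = 0.8 for B. In the strong case of run A the strata give 59.6 − 57.2 = 2.4 points and baseline area 66.8 − 59.6 = 7.2, about three quarters of the gain. Run B shows that the gain comes from the covariates and not from modelling both visits.

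**5. Type I error.** In run A the chi-square rejected in 4.0% to 5.0% of null trials and the strata-plus-area model in 5.0% to 5.5%. In run B all methods lay between 3.8% and 5.2%. The chi-square is valid, and slightly conservative when the covariates are strong.

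**6. What is estimated.** Week-4 success in run A was 0.698 v 0.500, 0.683 v 0.500 and 0.657 v 0.501 in the three cases. The conditional odds ratio of 2.3 thus corresponds to marginal odds ratios of 2.31, 2.16 and 1.91, or differences of about 20, 18 and 16 points.

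**7. Missing areas.** With an assumed 20% missing at random at week 4, a week-4 simulation gave chi-square power falling from 77/71/56% to 69/60/47%, and adjusted power from 76/74/66% to 69/63/57%. In the first two cases that loss (7 to 11 points) exceeds the gain from adjustment.

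**The case against.** A reader might infer that the trial defines one wound outcome and tests another. That is too strong. Section 2.6.2 says how the change in area is obtained, and 2.8 adds threshold, visit, groups and test. Percent reduction from baseline is the natural reading. What is missing is a formula and a reference visit, and leaving the deciding visit to the analysis section is not itself an error.

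A reader might also infer that an unadjusted test is wrong after stratified randomisation. The null rejection rates do not support this. Replacing it is a matter of efficiency: the strata alone add 0 to about 2 points, and the rest depends on prognostic effects for which the documents give no evidence. Nor is a repeated-measures GEE needed for the week-4 gain.

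Missing data can matter more than adjustment, and a definition that says nothing on missing areas or several ulcers per patient would still not be usable. That stands and is taken into the fix. The use of *admission* as time origin in 2.8 for a trial in outpatients (2.2) is wording only.

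The envelope sequence affects every baseline measure, not just this one. It is relevant here because baseline area is both denominator and proposed covariate. The documents do not show that the baseline measurement is biased, or that the person measuring knows the group. They only leave that possible.

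**Conclusion.** The planned chi-square is valid but leaves available baseline information unused. Week-8 wound areas have no planned analysis, the percentage that is tested lacks a written definition, and its denominator is measured after allocation is revealed. The gain from adjustment is about 0 points of power if the covariates are not prognostic, 2 to 3 if moderate and about 10 if strong, for 178 patients with complete data, 50% control success and a conditional odds ratio of 2.3. Roughly three quarters of it comes from baseline area. The text findings need no assumptions; the power figures rest on assumed inputs throughout.

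This is a cheap improvement. A reader might conclude that the trial's main inference is at risk. It is not: the sample size is built on quality of life, and the wound aim has one valid planned test.

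**What to change.** - **2.8, week 4.** Make the lead analysis a logistic regression of at least 50% area reduction from baseline on group, neuropathic ulcer, hemodialysis and log baseline area. Report the odds ratio and a standardised difference in proportions, each with a 95% CI. Keep the chi-square as a secondary, unadjusted result.
- **2.8, week 8.** Fit the same model as a supporting result. A logit GEE over both visits is an acceptable alternative. Treat shrinkage of any size as descriptive.
- **2.6.2.** Define percent reduction = 100 × (baseline area − follow-up area)/baseline area, with a closed wound counted as 100%. Name one prespecified index ulcer per patient, give a rule for missing areas under intention-to-treat, and time visits from baseline data collection.
- **2.7.** Measure the baseline wound before the envelope is opened.

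**Cost.** Wording, one more model, and a change in the order of baseline steps; no new data. Power falls by up to about 1 point if the covariates are not prognostic. The odds ratio becomes conditional (2.3 against a marginal 1.9 with strong covariates), hence the standardised difference. A Wald test on that difference rejected in 5.3% to 6.0% of null trials in run A, so the log-odds contrast should be the test and the difference the estimate. The plan names SPSS 20.0; whether it gives the standardised interval directly was not checked and should be confirmed first. If the adjusted model is declined, the changes to 2.6.2 and 2.7 and a stated role for week 8 are still worth making.
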